5.4.2.1 Dose modifications and treatment alterations for 5-FU

The dose of 5-FU will be modified, if the following toxicities (Table 3) are observed during the radiochemotherapy on the planned day of 5-FU infusion.

Once a 5-FU dose modification has occurred, the dosage may not be re-escalated for this patient. If therapy is delayed for longer than 2 weeks, the patient will be withdrawn from the study.

If on the day of planned 5-FU infusion one of the following toxicities occurs, a dose modification according to the following scheme will be performed:

Table 3: Dose modification for 5-FU in case of toxicities on the day of planned 5-FU infusion

Toxicity	CTC - Grade	Continue with Chemotherapy	Dose modification
Neutropenia	ANC $\geq 1.5 \times 10^9/L$	Yes	No
	ANC $< 1.5 \times 10^9/L$	Delay until ANC $\geq 1.5 \times 10^9/L$	No
	ANC $< 0.5 \times 10^9/L$	Delay until ANC $\geq 1.5 \times 10^9/L$	Yes 5-FU 75% of original dose
Thrombocytopenia	Platelets $\geq 100 \times 10^9/L$	Yes	No
	Platelets $< 100 \times 10^9/L$	Delay until platelets $\geq 100 \times 10^9/L$	No
	Platelets $< 25 \times 10^9/L$	Delay until platelets $\geq 100 \times 10^9/L$	Yes 5-FU 75% of original dose
Diarrhea	Grade 0-1	Yes	No
	Grade 2	Delay until resolved to grade < 2	No
	Grade 3	Delay until resolved to grade < 2	1 st occurrence: No 2 nd occurrence: Yes 5-FU 75% of original dose
	Grade 4	withdrawal	withdrawal
Mucositis/Stomatitis	Grade ≥ 1	Delay until resolved	Yes 5-FU 75% of original dose
Skin (except irradiated region and cetuximab-related skin toxicities)	Grade ≥ 2	Delay until grade 0-1	Yes 5-FU 75% of original dose
Further non-hematological toxicities (except nausea/vomiting and alopecia)	Grade 0-1	Yes	No
	Grade 2-3	Delay until grade 0-1	Yes 5-FU 75% of original dose
	Grade 4	withdrawal	withdrawal

If at any time during the radiochemotherapy one of the following toxicities occurs, a dose modification of 5-FU at the next planned infusion will be performed according to the following scheme:

Table 4: Dose modification for 5-FU in case of toxicities during radiochemotherapy

Toxicity	CTC-Grade	Dose modification
Neutropenia	ANC < 0.5 x 10 ⁹ /L	5-FU 75% of original dose
Thrombocytopenia	Platelets < 50 x10 ⁹ /l	5-FU 75% of original dose
Diarrhea	≥ Grad 3 (≥ stools/day or incontinence)	5-FU 75% of original dose
Nausea/vomiting	≥ Grad 3	5-FU 75% of original dose

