5.4.3 Cisplatin

5.4.3.1 Dose modifications and treatment alterations for cisplatin

Table 5: Dose modification regarding the cisplatin induced renal toxicity prior to every new course:

Creatinine value	Dose modification
≤ 1.5 mg/dl	no dose modification
> 1.5 mg/dl	Delay until creatinine is < 1.5 mg/dl, then restart with 50% of original dose

Additionally the following criteria have to be fulfilled prior to every chemotherapy course:

- Neutrophils ≥ 1,5 x 10⁹/L
- Thrombocytes ≥ 100 x 10⁹/L
- Diarrhea NCI-CTC Version 4.0 Grade < 2

If these parameters are not appropriately at the scheduled time point of the new course, cisplatin administration has to be discontinued until the criteria above will be fulfilled.

If cisplatin cannot be administered for less than two weeks, the therapy will be continued with the initial dosing.

If cisplatin cannot be administered for more than two weeks the administered dose will be 75% of the original value.

If at any time during the radiochemotherapy one of the following toxicities occurs, a dose modification of cisplatin at the next planned infusion will be performed according to the following scheme:

Table 6: Dose modification for cisplatin in case of toxicities during radiochemotherapy

Toxicity	CTC-Grade	Dose modification
Neutropenia	ANC < 0.5 x 10 ⁹ /L	Cisplatin 75% of original dose
Thrombocytopenia	Platelets < 25 x10 ⁹ /l	Cisplatin 75% of original dose
Further non-hematological toxicities (except nausea and vomiting)	Grade 3	Cisplatin 75% of original dose
	Grade 4	Discontinuation of chemotherapy

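### Table 4 lets 5-FU resume at 75% after grade 4 diarrhoea that resolved between infusions, where Table 6 appears to stop chemotherapy

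*Combined protocol and SAP*

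**What the plan says.** Three tables bear on diarrhoea and chemotherapy dosing.

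- **Table 3 (5.4.2.1)** covers findings on the infusion day. Its lead-in is "If on the day of planned 5-FU infusion one of the following toxicities occurs, a dose modification according to the following scheme". Grade 4 diarrhoea means withdrawal. Grades 2 and 3 mean delay until the grade is below 2.
- **Table 4 (5.4.2.1)** is introduced by "If at any time during the radiochemotherapy one of the following toxicities occurs, a dose modification of 5-FU at the next planned infusion". Its diarrhoea row is "≥ Grad 3 (≥ stools/day or incontinence" and the action is 5-FU at 75%. The stool count missing from that cell may be a loss in text extraction, and nothing here rests on it.
- **Table 6 (5.4.3.1)** has the same trigger, written for cisplatin: "If at any time during the radiochemotherapy one of the following toxicities occurs, a dose modification of cisplatin at the next planned infusion". It has no diarrhoea row. Its last category is "Further non-hematological toxicities (except nausea and vomiting"), and the action there for grade 4 is "Discontinuation of chemotherapy".

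Section 5.4.2.1 also makes a reduction permanent: "Once a 5-FU dose modification has occurred, the dosage may not be re-escalated for this patient". Section 4.2.4 requires withdrawal for any grade 4 toxicity related to cetuximab. For other adverse events it leaves withdrawal to the wish or judgement of the patient or investigator.

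**The concern.** Courses 1 and 2 start 28 days apart and courses 2 and 3 start 35 days apart (section 4.1). Diarrhoea can therefore reach grade 4 and settle before the next infusion day. Table 3 then finds nothing to act on, and Table 4 is the 5-FU table that applies. Read literally, it sends the patient back to 5-FU at 75%, and section 5.1.2 names diarrhoea among that drug's main adverse reactions. An investigator who also consults Table 6 finds an instruction to stop.

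Patient safety and consistency between centres are at stake. A patient with the same history could be stopped at one centre and treated again at another.

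**Working it through.** **Comparison of the instructions.** No figure in the plan needs reproducing here, so the check is of triggers and actions.

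| Situation | Table 3 | Table 4 | Table 6 |
|---|---|---|---|
| Grade 4 diarrhoea present on the infusion day | Withdrawal | Does not remove the Table 3 rule | Discontinue chemotherapy |
| Grade 4 diarrhoea that arose and resolved between infusions | Not triggered | 5-FU at 75% at next infusion | Discontinue chemotherapy |

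The conflict is in the second row, and it rests on three steps.

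1. A threshold of grade 3 or higher with no upper limit includes grade 4.
2. Diarrhoea falls in the non-haematological row of Table 6, because it has no row of its own there and only nausea and vomiting are exempt.
3. The Table 6 action reaches 5-FU only if *chemotherapy* means both drugs. The other action cells in that table name cisplatin; only the grade 4 cell changes to chemotherapy. Section 5.3.2, headed as chemotherapy administration, covers 5-FU and cisplatin together. Section 5.1.1.2 uses the term for the infusions of both drugs after cetuximab.

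Table 4's nausea and vomiting row is also open-ended, but it creates no such conflict, because Tables 3 and 6 both exempt those events.

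**5-FU at stake.** Section 4.1 plans four days of 1000 mg/m²/day in courses 1 and 2, and four days of 750 mg/m²/day in courses 3 and 4. The original dose in courses 3 and 4 could mean the planned 750 or the starting 1000, so both are shown.

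- Course 2 at 75%: 4 × 750 = 3000 mg/m².
- Courses 3 and 4 at 75%, each: 4 × 562.5 = 2250 mg/m² (from 750), or 4 × 750 = 3000 mg/m² (from 1000).
- Event after course 1, courses 2 to 4 all given: 3000 + 2 × 2250 = 7500, up to 3000 + 2 × 3000 = 9000 mg/m².
- Event after course 1, patient goes to surgery: 3000 mg/m² (course 2 only). Course 2 starts after 20 fractions × 1.8 Gy = 36 Gy, before the stop at 45 Gy (25 fractions).
- Event after course 2, courses 3 and 4 given: 2 × 2250 = 4500, up to 2 × 3000 = 6000 mg/m².
- Under Table 6, if it includes 5-FU: 0.

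**How often.** The documents give no grade 4 diarrhoea rate. Section 2.3.2.1 cites a randomised phase II chemotherapy trial without radiotherapy, with grade 3/4 diarrhoea in 16% with cetuximab plus cisplatin/5-FU and 0% without. Taking 16% for arm A as an assumption:

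- Whole trial, 33 to 39 patients per arm (Table 10): 0.16 × 33 = 5.3, to 0.16 × 39 = 6.2 patients with grade 3 or 4.
- Patients still to come (section 8.4: 66 treated, 72 to 78 expected): 72 − 66 = 6, to 78 − 66 = 12. With half in arm A, that is 3 to 6 patients, and 0.16 × 3 = 0.5 to 0.16 × 6 = 1.0 with grade 3 or 4.

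Grade 4 is an unknown part of these counts.

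**The case against.** The strongest reply is that Table 6 belongs to the cisplatin section and its lead-in speaks of cisplatin, so one word carries its effect on 5-FU. That is true, and the conflict between Tables 4 and 6 depends on it. Even on a cisplatin-only reading, an oddity remains: grade 4 diarrhoea still present on the infusion day ends treatment, while grade 4 that settled beforehand leads to 5-FU at 75%.

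A second reply is that the tables can be reconciled. Table 4 sets the dose at the next planned infusion, and after discontinuation none is planned. This works, but only for a reader who consults the cisplatin table before dosing 5-FU. It also reaches the same result as the proposed change.

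A third reply points to safeguards. A life-threatening event is reported to the sponsor at once (6.1.1.3, 6.1.3), the investigator may withdraw the patient (4.2.4), and section 5.1.2 refers to the 5-FU product information. These reduce the risk. None states that it overrides the tables, and section 2.5 names section 5.4 as the source of 5-FU modifications.

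The frequency estimate is also weak. In the cited trial all the grade 3/4 diarrhoea occurred with cetuximab, and in arm A any case attributed to cetuximab already requires withdrawal under 4.2.4. The gap is left for arm B and for arm A cases not attributed to cetuximab.

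A reader might infer two stronger points that the documents do not support. One is that a patient with active grade 4 diarrhoea would be infused; Table 3 requires withdrawal on that day. The other is that no rule governs infusion-day findings; two sentences and a caption in 5.4.2.1 assign them to Table 3. It is true only that Table 4's trigger does not expressly exclude that day.

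**Conclusion.** The point holds in a narrow form. For grade 4 diarrhoea that arises and resolves between infusions, Table 4 permits 5-FU at 75%, and Table 6 most naturally read forbids it. Section 4.2.4 does not decide between them unless the toxicity is related to cetuximab.

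For such a patient the difference is 3000 to 9000 mg/m² of further 5-FU after an event following course 1, or 4500 to 6000 mg/m² after an event following course 2, against none. The figures above 3000 assume that every later course is given. The number of patients is unknown, probably small, and may be zero among those still to be randomised. The case for acting rests on the consequence for a patient, not on frequency. The primary analysis and sample size are not touched. The conclusion assumes that *chemotherapy* in Table 6 includes 5-FU, which the wording suggests but does not state.

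**What to change.** In Table 4, change the diarrhoea row to *Grade 3* and add: *Grade 4 diarrhoea at any time: withdrawal from chemotherapy (see Tables 3 and 6).*

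This should not be extended into a rule that Table 4 alone governs any toxicity that began between infusions. Table 4 has no delay column, so such a rule would remove Table 3's delay for a toxicity that persists to the infusion day. Any further clarification must keep Table 3's delay and withdrawal rules in force for everything still present on that day, whenever it began.

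The cost is a short amendment. Section 12.5 requires ethics committee approval before it takes effect, and patient consent where it affects the patient. It would apply to about 6 to 12 further patients and to any still on treatment; those already treated followed the existing text. If Table 6 already includes 5-FU, the change adds no stops that the protocol does not already require. If the sponsor intended Table 6 to stop cisplatin alone, the change would newly end 5-FU after resolved grade 4 diarrhoea, so the sponsor should confirm the intent when amending.

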5.4.3 Cisplatin

5.4.3.1 Dose modifications and treatment alterations for cisplatin

Table 5: Dose modification regarding the cisplatin induced renal toxicity prior to every new course:

Creatinine value	Dose modification
≤ 1.5 mg/dl	no dose modification
> 1.5 mg/dl	Delay until creatinine is < 1.5 mg/dl, then restart with 50% of original dose

Additionally the following criteria have to be fulfilled prior to every chemotherapy course:

- Neutrophils ≥ 1,5 x 10⁹/L
- Thrombocytes ≥ 100 x 10⁹/L
- Diarrhea NCI-CTC Version 4.0 Grade < 2

If these parameters are not appropriately at the scheduled time point of the new course, cisplatin administration has to be discontinued until the criteria above will be fulfilled.

If cisplatin cannot be administered for less than two weeks, the therapy will be continued with the initial dosing.

If cisplatin cannot be administered for more than two weeks the administered dose will be 75% of the original value.

If at any time during the radiochemotherapy one of the following toxicities occurs, a dose modification of cisplatin at the next planned infusion will be performed according to the following scheme:

Table 6: Dose modification for cisplatin in case of toxicities during radiochemotherapy

Toxicity	CTC-Grade	Dose modification
Neutropenia	ANC < 0.5 x 10 ⁹ /L	Cisplatin 75% of original dose
Thrombocytopenia	Platelets < 25 x10 ⁹ /l	Cisplatin 75% of original dose
Further non-hematological toxicities (except nausea and vomiting)	Grade 3	Cisplatin 75% of original dose
	Grade 4	Discontinuation of chemotherapy

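### Section 5.4.3.1 gives two cisplatin doses (80 or 60 mg/m² per course) when a course is held for under two weeks and ANC < 0.5 or platelets < 25 occurred, with no rule on which prevails

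*Combined protocol and SAP*

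**What the plan says.** Section 5.4.3.1 contains several cisplatin rules.

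- **Renal rule (Table 5).** Its heading is "Dose modification regarding the cisplatin induced renal toxicity prior to every new course". Creatinine up to 1.5 mg/dl needs no change; above that the instruction is "Delay until creatinine is < 1.5 mg/dl, then restart with 50% of original dose".
- **Start criteria.** "Additionally the following criteria have to be fulfilled prior to every chemotherapy course": neutrophils at least 1.5 × 10⁹/L, platelets at least 100 × 10⁹/L, diarrhea below grade 2. If they are not met, cisplatin waits until they are.
- **Short hold.** "If cisplatin cannot be administered for less than two weeks, the therapy will be continued with the initial dosing".
- **Long hold.** "If cisplatin cannot be administered for more than two weeks the administered dose will be 75% of the original value".
- **Severe toxicity (Table 6).** If a listed toxicity occurs at any point in radiochemotherapy, "a dose modification of cisplatin at the next planned infusion will be performed". For ANC < 0.5 or platelets < 25 (× 10⁹/L) the entry is "Cisplatin 75% of original dose".

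The section does not rank these rules. It also does not say whether a reduced cisplatin dose is kept. By contrast, section 5.4.2.1 bars re-escalation of 5-FU, and section 5.4.1.1 makes cetuximab reductions permanent.

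**The concern.** The short-hold sentence and Table 6 can both apply to one patient, and they name different doses. The short-hold sentence looks only at the length of the delay, Table 6 only at the depth of the toxicity. A site that follows the first gives full-dose cisplatin after a very low neutrophil or platelet count; a site that follows the second gives three quarters. About 15 centers are planned, and each could settle the question differently.

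The trigger matters clinically. Section 5.3.1 warns that cetuximab with platinum-based chemotherapy raises the risk of severe neutropenia and of infections that follow from it. At stake are patient safety and uniform dosing. No sample size or error rate is involved.

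**Working it through.** The plan gives no figure to reproduce. The check is to apply each rule to the same case.

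**Doses.** Section 4.1 gives 20 mg/m²/day for 4 days.

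- Full course: 20 × 4 = 80 mg/m².
- 75%: 0.75 × 80 = 60 mg/m² (15 mg/m²/day).
- 50%: 0.50 × 80 = 40 mg/m².

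**A patient who meets both rules.** Hematology is weekly (section 7.2.1), and course 2 in arm B is due on day 29. Suppose ANC is 0.4 on day 22, 1.2 on day 29, and at least 1.5 on day 36.

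- Day 29 fails the start criterion, so the course is held for 36 − 29 = 7 days, under two weeks. The short-hold sentence gives 80 mg/m².
- ANC of 0.4 on day 22 is below 0.5, and course 2 is the next planned infusion. Table 6 gives 60 mg/m².
- Difference: 80 − 60 = 20 mg/m², and 20/80 = 25% of the course.

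An ANC of 0.4 on the due day itself, or platelets below 25, leads to the same conflict.

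**Scope.** Table 6 is limited to toxicity during radiochemotherapy. The synopsis gives 6.5 to 7 weeks for that phase (about 46 to 49 days), while section 7.3 uses a similar term for the whole treatment. Section 5.5.1 starts radiotherapy on the first chemotherapy day. Counted from there, courses fall due on days 1, 29, 64 and 92 in both arms (arm A: study days 8, 36, 71 and 99, each minus 7). Course 2 held for up to 13 days restarts by day 29 + 13 = 42, inside the shorter phase. The conflict at course 2 therefore does not depend on the definition. For a severe count first seen on the due day of course 3 or 4, it arises only under the wider meaning. Patients found resectable stop after 45 Gy (section 7.2.3) and may never receive the held course.

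**Comparison with 5-FU.** Table 3 in section 5.4.2.1 separates the tiers. ANC below 1.5 or platelets below 100 means delay only; ANC below 0.5 or platelets below 25 means delay plus 75%. Section 5.4.3.1 lacks this separation.

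**Long holds.** Beyond two weeks, the long-hold sentence and Table 6 both give 75%, so section 5.4.3.1 agrees with itself. The conflict is with section 5.4.2.1, which takes the patient off study once *therapy* is delayed beyond 2 weeks. Its rules cover toxicities "observed during the radiochemotherapy on the planned day of 5-FU infusion". Both drugs are due on the same days and share the neutrophil, platelet and diarrhea thresholds, so at least at course 2 one hold can set off both rules: 60 mg/m² or withdrawal.

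**Re-escalation.** Take a patient cut to 50% for creatinine who comes to the next course with creatinine at most 1.5 mg/dl and no new toxicity. If the cut is kept, the dose is 40 mg/m². If Table 5 is applied afresh, it is 80 mg/m².

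**The case against.** The strongest reply is that the section already reads sensibly. The hold sentences deal with delays after mild threshold failures; Table 6 adds a mandatory rule for severe events; and the specific rule governs the general one. The 5-FU tiers support this. As an account of what was meant, it is probably right. But the short-hold sentence carries no condition, and no line ranks Table 6 above it.

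The consequence is also limited. Counts must recover before restart, no reading exceeds the planned 20 mg/m²/day, and both arms share the rules. Section 8.4 reports 66 patients already randomized and treated by the end of July against an expected Full Analysis Set of 72 to 78, so about 72 − 66 = 6 to 78 − 66 = 12 more, plus any still on treatment. All of this stands and keeps the point modest. Section 5.1.3 refers investigators to the product information for dose modifications, but that does not settle a conflict within the protocol.

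A reader might infer more than the documents support:

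- *Holds over two weeks have no cisplatin dose.* They do: 75%. Only the conflict with section 5.4.2.1 remains. The withdrawal sentence there sits among 5-FU rules and may mean 5-FU alone. The withdrawal list in section 4.2.4 names a cetuximab delay but no chemotherapy delay, which does not settle it.
- *After a renal cut the next course could equally be 60 mg/m².* That needs a separate Table 6 toxicity. On unchanged facts the readings are 40 and 80, and the Table 5 heading favors a fresh assessment each course.
- *Grade 3 diarrhea creates the same conflict.* This is only arguable. Table 6 does not name diarrhea, and Table 3 keeps it apart from other non-hematological toxicities.

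**Conclusion.** The contradiction is real but narrow. For a hold of under two weeks with ANC < 0.5 or platelets < 25 during radiochemotherapy, section 5.4.3.1 supports both 80 and 60 mg/m² for the course, and a site following the short-hold sentence gives the higher dose after severe marrow toxicity. It should be fixed because it is a conflict in a dosing instruction and the remedy is short.

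The long-hold conflict with section 5.4.2.1 and the missing re-escalation rule are secondary.

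The conclusion rests on the rules as written and needs no assumption about event rates. The documents give no frequency for these events, so the number of affected patients cannot be stated. They do not support inferring harm to the primary analysis: no effect on 2-year overall survival is shown. Section 5.3.1 suggests the trigger could be commoner in arm A, but nothing in the documents sizes this.

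**What to change.** In section 5.4.3.1, state that after a hold of under two weeks the initial dosing resumes only if neither Table 5 nor Table 6 calls for a reduction, and that otherwise the lowest applicable dose is given. This matches the tiers already used for 5-FU.

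In the same edit:

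- Limit the withdrawal sentence in section 5.4.2.1 to 5-FU, or align it with the 75% restart for cisplatin.
- State whether a reduced cisplatin dose may be raised again. Whether renal reductions are kept or reassessed at each course is for the sponsor's clinicians to decide.

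The cost is a few sentences and a short notice to sites, with no extra patients or assessments. The change may count as a protocol amendment under section 12.5. It would then need a favorable opinion from the ethics committees before use and, if it affects patients, their consent.

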2.3.2.3 Cetuximab general safety information

Adverse event data are available for 3339 patients treated with cetuximab alone or in combination with chemotherapy and/or radiation therapy from investigational trials across all indications conducted by ImClone, BMS, Merck KGaA, Investigator sponsored Trials (IST), Cooperative Groups and the National Cancer Institute (NCI). As most of the trials were conducted under different settings and in combination with various cytostatic therapies, adverse reaction rates cannot be validly pooled and quoted as mean rates. Nevertheless, they constitute a basis for identifying approximate adverse event rates associated with the administration of Cetuximab.

Skin reactions may develop in more than 80% of patients and mainly present as acne-like rash and/or, less frequently, as pruritus, dry skin, desquamation, hypertrichosis, or nail disorders (e.g. paronychia). The majority of skin reactions develop within the first three weeks of therapy. They generally resolve, without sequelae, over time following cessation of treatment if the recommended adjustments in dose regimen are followed [45]. Approximately 15% of the skin reactions are severe, including single cases of skin necrosis. In the event of Grade 3 or 4 skin reactions the patients should be referred for dermatological advice.

The incidence of radiation dermatitis of any grade was comparable between the treatment groups in a phase 3 SCCHN trial in patients receiving either cetuximab in combination with RT (86%) or RT alone (90%) [46].

Other side effects observed in patients receiving cetuximab monotherapy include asthenia, dyspnoea, mucositis, nausea, pain, fever and headache.

Mild or moderate infusion-related reactions may occur ($\geq 1/10$) comprising symptoms such as fever, chills, nausea, vomiting, headache, dizziness, or dyspnoea that occur in a close temporal relationship mainly to the first cetuximab infusion [45]. They can be managed by

slowing the infusion rate of cetuximab and by the continued use of pre- medications for subsequent doses in addition to the mandatory use for the first infusion.

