4.1 Overall study design and plan

This is an open-label, randomized Phase II-study to evaluate immuno-radiochemotherapy in patients with unresectable esophageal cancer.

Up to approximately 15 German centers will participate in the trial (up to 134 patients). However, the randomization to one of the two treatment groups will be stopped at December 31, 2016, at the latest, which is 2.5 years later than originally planned.

Eligible patients will have a diagnosis of histologically confirmed locally advanced initially unresectable esophageal cancer.

Resectability has to be defined and documented by a surgeon prior to randomisation:

The tumor is considered unresectable due to:

- T-stage
- N-stage
- Performance status/Nutritional status
- Comorbidity:
 - Pulmonary function
 - Other
- Tumor location
 - Upper third of the esophagus
 - Relation to other organs/structures
- Other reasons (please define in CRF)

Patients will be randomized into two treatment arms (Arm A and B) and according to this treated plus or minus cetuximab.

Patients in Arm A will receive cetuximab with concurrent radiochemotherapy as follows:

- Cetuximab initial dose of 400 mg/m² (day 1), followed by weekly doses of 250 mg/m² for a total of 14 weeks.
- 5-FU: 1000 mg/m²/day* administered as continuous infusion over 4 days at the beginning of course 1 and 2, i.e. on days 8-11 and 36-39. 750 mg/m²/day administered as continuous infusion over 4 days at the beginning of course 3 and 4, i.e. on days 71-74 and 99-102. The time period between course 2 and 3 is prolonged to 5 weeks.
- Cisplatin (20 mg/m²/day) administered as intravenous bolus over 60 minutes on days 1-4 at the beginning of each course, i.e. on days 8-11, 36-39, 71-74 and 99-102.
- Radiotherapy: 59.4 Gy (33 fractions of 1.8 Gy) will be administered over 6.5 - 7 weeks (5 x 1.8 Gy per week) to the primary tumor and the involved lymph nodes. 50,4 Gy will be administered to the loco-regional lymph nodes (mediastinum). If resectability has been achieved after 4-4.5 weeks (36-41.4 Gy), radiotherapy will be stopped at 45 Gy and patient will undergo surgery.

**Safe dose level identified in the earlier phase I-study (LEOPARD Phase I)*

Patients in Arm B will be treated with radiochemotherapy as follows without receiving cetuximab:

:

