5.4.1.3 Other reasons for cetuximab discontinuation

If a subject develops an intercurrent illness (i.e., infection) that, in the opinion of the investigator mandates interruption of cetuximab therapy, that intercurrent illness must resolve within a time frame such that no more than two consecutive infusions are withheld. After the interruption of treatment, the subject will continue with a cetuximab dose of 250 mg/m² at subsequent visits or the last dose before the interruption if there have been previous dose reductions.

If therapy must be withheld for a longer period of time, the subject will be removed from the study treatment. In special cases, the investigator may request that the patient continues to receive cetuximab (the investigator must ask permission from the Investigator-Sponsor).

5.4.2 5-Fluorouracil

Toxicities solely related to chemotherapy do not lead to a dose modification or interruption of cetuximab and vice versa.

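### For a grade 3 skin reaction due solely to cetuximab, Table 6 requires a cisplatin reduction that section 5.4.2 rules out, and nothing says which rule governs

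*Combined protocol and SAP*

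**What the plan says.** Four parts of section 5.4 bear on a grade 3 skin reaction caused by cetuximab.

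- **Table 6 (5.4.3.1, cisplatin).** If a listed toxicity arises at any point in radiochemotherapy, "a dose modification of cisplatin at the next planned infusion will be performed according to the following scheme". After rows for neutropenia and thrombocytopenia comes the row "Further non-hematological toxicities (except nausea and vomiting"). It sets cisplatin at 75% of the original dose for grade 3 and stops chemotherapy for grade 4. There is no skin row and no exception by cause.
- **Section 5.4.2 (under the 5-FU heading).** "Toxicities solely related to chemotherapy do not lead to a dose modification or interruption of cetuximab and vice versa".
- **Table 3 (5.4.2.1, 5-FU on the planned infusion day).** Skin has its own row: "Skin (except irradiated region and cetuximab-related skin toxicities"). Table 4, which covers 5-FU for toxicity arising during radiochemotherapy, has no skin row.
- **Section 5.4.1.1.** Grade 3 skin toxicity from cetuximab is managed by delaying, reducing or stopping cetuximab.

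Cetuximab is given in one arm only. Section 4.1 states: "Patients in Arm B will be treated with radiochemotherapy as follows without receiving cetuximab". Both arms are otherwise assigned the same cisplatin: "Cisplatin (20 mg/m²/day) administered as intravenous bolus over 60 minutes on days 1-4 at the beginning of each course".

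**The concern.** For one foreseeable event, mandatory passages give different instructions. A site that applies Table 6 reduces cisplatin. A site that applies section 5.4.2 does not. Both can say that they followed the protocol, and about 15 centers take part.

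The inconsistency is also one-sided by arm. The trial assesses cetuximab added to a common radiochemotherapy backbone, and section 8.3.3 justifies the randomized control arm by the two arms being handled alike. A reduction triggered by a toxicity that only cetuximab causes can occur only in arm A. How often it occurs would depend partly on which passage a site reads. At stake are uniform conduct and a clear description of the regimen that arm A received.

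**Working it through.** The plan gives no figure on this point to reproduce. The check is a comparison of texts, followed by an illustrative size.

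**Step 1. One event, each rule.** Take a grade 3 acne-like rash due solely to cetuximab.

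| Passage | 5-FU | Cisplatin |
|---|---|---|
| Table 3 | not reduced (excepted) | not addressed |
| Table 4 | no skin trigger | not addressed |
| 5.4.2, reverse direction | not modified | not modified, if the sentence covers all chemotherapy |
| Table 6 | not addressed | 75% at the next infusion |

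The only Table 6 rows above the non-haematological row are two blood counts, so the word *further* takes in skin. The cisplatin section neither repeats nor cites section 5.4.2. Grade 4 adds little: section 4.2.4 already withdraws patients with grade 4 cetuximab-related toxicity from study treatment.

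**Step 2. Planned cisplatin (4.1).** 20 mg/m² × 4 days × 4 courses = 320 mg/m², or 80 mg/m² per course. A course at 75% is 60 mg/m², a loss of 20 mg/m².

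**Step 3. Loss per affected patient.** Section 2.3.2.3 places most skin reactions in the first three weeks, before arm A's course 2 on day 36. I read the next planned infusion as the next course.

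- One course reduced: 20/320 = 6.25%.
- Courses 2 to 4 reduced: 60/320 = 18.75%.

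Table 6 does not say whether the reduction persists. The bar on re-escalation in 5.4.2.1 is stated for 5-FU only.

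**Step 4. Assumed rate of grade 3 skin reactions.**

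- Lower value: 6%, the grade 3/4 rash rate (against 0%) in the randomized phase II of cisplatin and 5-FU with or without cetuximab cited in 2.3.2.1.
- Upper value: section 2.3.2.3 says "Skin reactions may develop in more than 80% of patients" and "Approximately 15% of the skin reactions are severe, including single cases of skin necrosis". This gives 0.80 × 0.15 = 12%.

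Both are assumptions. Either may include grade 4, and section 2.3.2.3 itself cautions against pooling its rates.

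**Step 5. Patients affected in arm A (33-36 per arm, synopsis).**

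- 6%: 0.06 × 33 = 2.0; 0.06 × 36 = 2.2.
- 12%: 0.12 × 33 = 4.0; 0.12 × 36 = 4.3.
- Chance of at least one case: 1 − 0.94^33 = 87% up to 1 − 0.88^36 = 99%.
- Arm B from this cause: 0.

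**Step 6. Mean loss across arm A.**

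- Lowest: 0.06 × 6.25% = 0.375%, about 0.4%.
- Highest: 0.12 × 18.75% = 2.25%, about 2.3%.

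**Step 7. Cases still to come.** Section 8.4 counts 66 patients already randomized and treated, with 72-78 expected in the Full Analysis Set. That leaves 6-12 patients, or 3-6 in arm A. Expected new cases: 3 × 0.06 = 0.2 to 6 × 0.12 = 0.7, plus any among patients still on treatment.

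**The case against.** The strongest reply is that section 5.4.2 already settles the matter. It speaks of chemotherapy, which includes cisplatin, and section 5.4.1.1 handles cetuximab rash through cetuximab alone, so Table 6 can be read as subject to it. That reading is open to a site, but the text does not compel it. The sentence stands under the 5-FU heading, the cisplatin section does not refer to it, and Table 6 is specific and mandatory. Had the general sentence been enough, Table 3 would not have needed its own exception.

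A second reply is that drug-specific tables need not match. Table 3 concerns the infusion day and Table 6 any time during treatment; Tables 4 and 6 also use different platelet limits (50 and 25 × 10⁹/L). This stands: a difference between Tables 3 and 6 is not by itself a contradiction. The conflict lies between Table 6 and section 5.4.2. Table 3 shows that the issue was foreseen for 5-FU.

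It also limits what can be said about dermatitis in the irradiated field, which Table 3 excepts and Table 6 does not. A reader might count this as a further breach of section 5.4.2. It is not one, because that section addresses only cetuximab and chemotherapy. Nor is it shown to be one-sided: section 2.3.2.3 reports radiation dermatitis in 86% with cetuximab and 90% without in a head and neck trial. It is a separate difference between the two drug tables that can affect both arms.

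A third reply is that little can now be prevented. Step 7 of the working bears this out for future dosing, but not for describing what patients already treated received.

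**Conclusion.** The contradiction is real and in the current text. For toxicity due solely to cetuximab, Table 6 requires a cisplatin reduction, section 5.4.2 says chemotherapy is not modified, and no passage ranks them. Any reduction from this cause falls in arm A alone.

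Its likely size is small and rests on three assumptions: a grade 3 skin rate of 6% to 12%, sites applying Table 6 literally, and one to three reduced courses. The upper end needs a persistent reduction that Table 6 does not state. Patients who become resectable and stop at 45 Gy would lose less.

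Two stronger readings are tempting, and the documents support neither. A reader might infer that arm A patients lose cisplatin altogether; at grade 3 the rule is a reduction to 75%. A reader might also infer that the 2-year survival comparison is confounded. A dose change brought about by assigned cetuximab is a consequence of treatment after randomization, not a confounder. At a mean loss of 0.4% to 2.3% no material effect on survival is shown, and no sample size or power figure depends on it.

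**What to change.** The sponsor must reconcile Table 6, section 5.4.2 and Table 3 for toxicity due solely to cetuximab, and state which passage governs cisplatin. Which rule stands is for the sponsor's clinicians. The same edit should say whether the tables' different treatment of the irradiated region is intended, and whether a Table 6 reduction applies to one course or to all that follow.

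For the analysis, report by arm the chemotherapy reductions attributed to cetuximab toxicity, including in patients already treated. Section 6.1.2 already records causal relationship to cetuximab or chemotherapy, and chemotherapy dose reduction as an action taken. As listed, that action does not name the drug, so flagged cases may need a check against dosing records.

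The cost is a small edit to section 5.4 and one table in the report, with no new data item. If the edit counts as a major change, section 12.5 requires an amendment and ethics committee approval before it takes effect. The tabulation can go ahead without that change.
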